9.2.3 Suspected unexpected serious adverse reactions (SUSARs)

Not applicable.

9.3 Annual safety report

Not applicable.

9.4 Follow-up of adverse events

All AEs will be followed until they have abated, or until a stable situation has been reached. Depending on the event, follow up may require additional tests or medical procedures as indicated, and/or referral to the general physician or a medical specialist. SAEs need to be reported till end of study within the Netherlands, as defined in the protocol

9.5 Data Safety Monitoring Board (DSMB)

Although this study does not add extra risks to the safety of the patients, we propose to compose an external DSMB because of the vulnerability of the population and the complicated logistics of the study. The DSMB will monitor the safety, validity and credibility of the trial in order to protect the patients and will provide the trial's Steering Committee with recommendations regarding continuation or cessation of the trial. The composition, tasks, responsibilities and working procedures of the DSMB are described in the DSMB charter. The DSMB will meet to discuss the findings of the interim analyses. These will be conducted when the data of 25%, 50% and 75% of the inclusions have been gathered. The DSMB will assess safety, not futility. In principle, the trial will not be stopped early for beneficial effect on the primary outcome. During the closed DSMB meetings, the data manager will be stand-by to reveal any additional data if the DSMB thinks this is necessary. The advice(s) of the DSMB will only be sent to the sponsor of the study. Should the sponsor decide not to fully implement the advice of the DSMB, the sponsor will send the advice to the reviewing METC, including a note to substantiate why (part of) the advice of the DSMB will not be followed.

The DSMB will be composed of 3 individuals:

- [name], pharmacist/researcher, department of Respiratory Diseases, AMC Amsterdam
- [name], pediatrician/neonatologist, Chief Medical Officer at Bambi Medical
-
- [name], biostatisticus, UMC Utrecht
- [name], biostatisticus UMC Utrecht

The Steering Committee will propose a detailed mandate and review this with the DSMB. Identification and circulation of external evidence (e.g. from other trials or systematic

reviews) is not the responsibility of the members of the DSMB. It is the responsibility of the coordinating principal investigator to provide any such information to the DSMB.

10. STATISTICAL ANALYSIS

Analyses will be performed on an intention-to-treat (ITT) basis. The ITT population includes all randomised infants, regardless of protocol deviations, and includes patients with a signed informed consent for the study who have been randomised.

Descriptive statistics will be used to describe the characteristics of the study population. Means and standard deviations will be reported (normal continuous distributed data) or medians and interquartile range (skewed continuous variables). Categorical data will be presented as percentages.

In case of missing data, every attempt will be undertaken to retrieve the data by contacting NICUs and general hospitals where the child has been admitted and by contacting the child consultation clinic (with permission of the caregivers). Missing data, if >10%, will be assumed to be missing at random and multiple imputations will be used. We do expect less than 10% missing data for the primary endpoint, weight SDS.

Significance level will be 0.05.

All analyses will be completed with the statistical software package R (free download from www.rproject.org), and SPSS/PC Statistics 21.0 (SPSS Inc., Chicago, IL, USA).

Field (

10.1 Primary study parameter(s)

The primary endpoint is weight SDS at 6 months corrected age. Comparison between the two groups for this primary endpoint will be made using a mixed effect model with a random intercept to account for the correlation between the patients that come from the same hospital cluster.

10.2 Secondary study parameter(s)

All secondary parameters will be assessed by linear mixed effect models for continuous outcomes or logistic mixed effect models for binary outcomes. BPD severity and weight at inclusion are considered relevant variables for the outcome weight SDS at 6 months. These variables will be included in the mixed model analysis as fixed effects.

Secondary outcomes are:

- Rates of re-hospitalisations: the rates of re-hospitalisations between the 2 groups will be assessed.
- Quality of life of the caregivers (Dutch version of the CarerQOL questionnaire) (34)
Changes in the total score of the CarerQOL between baseline and 6 months and between baseline and 12 months will be assessed.

- Infant stress (Infant Behaviour Questionnaire – Revised, IBQ-R) (35): changes in the total score of the IBQ-R between baseline and 6 months and between baseline and 12 months will be assessed.
- Weight SDS, Length SDS, Head circumference SDS at 12 months corrected age, length SDS and head circumference SDS at 6 months corrected age: comparison between the two groups for these endpoints will be made.
- Length of hospital stay, length of oxygen supplementation: comparison between the two groups will be made.
- Unscheduled health care visits to the emergency department, general practitioner or paediatrician: comparison between the 2 groups will be assessed.

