Study population: Children born < 32 weeks of gestational age with moderate or severe BPD, will be included between 36 and 38 weeks of PMA. BPD will be defined as oxygen need for ≥ 28 days from birth until 36 weeks of PMA. BPD severity will be assessed at 36 weeks PMA. Children who, at that time, need ≥ 30% supplemental oxygen or depend on nasal continuous positive airway pressure (nCPAP), high flow nasal cannula oxygen (HFNC) or mechanical ventilation are classified as having severe BPD. If children need >21% oxygen but < 30% they are classified as having moderate BPD. If needed, an oxygen reduction test will be performed to assess BPD severity. (3)

Intervention: weaning of supplemental oxygen based on a lower SpO₂ limit of 95% as compared to 90% (usual care).

Main study parameters/endpoints: The primary outcome is body weight at 6 months corrected age, as a surrogate for lung growth. Secondary outcomes are weight and height at 12 months corrected age, hospital re-admissions, parental quality of life, infant stress, length of hospital stay, duration of oxygen supplementation and unscheduled health care visits. Lung function and CT scores will be measured in a subgroup of patients. A cost-effectiveness analysis will be performed alongside this trial.

Nature and extent of the burden and risks associated with participation, benefit and group relatedness:

The burden and risks associated with participation in the study are limited. There are no extra visits to the hospital as the 2 visits follow the routine follow-up of patients born extremely preterm. At every visit weight, height and head circumference are measured, which is routine care. In a subgroup of patients lung function tests and/or a free breathing CT scan of the chest will be performed, only if these tests are routine care in the specific hospitals. The parents will be asked to fill in 2 questionnaires (CarerQOL and IBQ-R) at inclusion, 6 and 12 months. Parents will have the possibility to record data on respiratory complaints, admissions, and absence from work in an online monthly diary.

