The risks of the study are negligible as the lower limit of 90% is considered usual care. Also, in a study in *younger* children from 32 weeks PMA onwards there was no difference in endpoints (growth, neurodevelopmental outcome) between a lower (91-94%) and a higher (95-98%) SpO₂ target. (4) Our study includes children with an established diagnosis of BPD, from 36 weeks PMA onwards, which is the period that alveolarization starts, which implies that SpO₂ limits may be different in this group. Potential benefit of the study is that weaning of oxygen is performed in a controlled and well-monitored way with frequent feedback to treating physicians and/or parents. A disadvantage of the study may be that children in the high SpO₂ group will be longer on oxygen, whether in the hospital or at home. In the study by Askie et al length of hospital stay was not different for the high versus low SpO₂ group. (4)

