3. STUDY DESIGN

This is a multi-centre randomised controlled, open study in children with moderate-severe BPD from 36 weeks PMA onwards with two parallel arms:

[figure not shown]
1. weaning of supplemental oxygen based on SpO₂ lower limit ≥ 95%
2. weaning of supplemental oxygen based on SpO₂ lower limit ≥ 90%.

This is a non-blinded study because we considered it not feasible to blind parents and treating physicians for SpO₂, as supplemental oxygen will be weaned based on SpO₂.

Study duration for each patient will be one year with three visits: at inclusion and at 6 and 12 months corrected age.

Setting of the study: patients will be included between 36 and 38 weeks PMA, when they are still admitted on the NICU or post-IC-high care units. Follow up will be alongside neonatal follow up pathways at outpatient clinics.

Study design:

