The Care-related Quality of Life instrument (CarerQol) is designed to measure and value the impact of providing informal care on carers. (34) It combines a subjective burden measure that provides a comprehensive description of the caregiving situation (CarerQol-7D) with a valuation of informal care in terms of well-being (CarerQol-VAS) (www.imta.nl). The Dutch version of the CarerQol will be used in this study, which is a 7 question and 1 page questionnaire which includes a Visual Analogue Scale. This CarerQol will be assessed during all visits and online monthly.

Weight, height, head circumference

At every visit weight, height and head circumference are measured. This is according to standard care.

IBQ-R

The Infant Behavior Questionnaire – Revised (IBQ-R), very short form, Dutch version is an instrument assessing 36 items on 3 broad scales of infant temperament. (36) The questionnaire assesses 6 domains: activity level, soothability, fear, distress to limitations, smiling and laughter and duration of orienting. The items on the IBQ-R ask parents to rate the frequency of specific temperament-related behaviors observed over the past week.

The IBQ-R is a research tool and will be assessed at all visits (0,6 and 12 months).

Multiple Breath Washout (MBW)

If available in the local NICU/ high care centre, lung clearance index (LCI) and functional residual capacity (FRC) will be measured with SF₆ as a tracer gas (Exhalyzer, Ecomedics, Switzerland) as routine clinical care at 6 months and/or 12 months corrected age. In short, the measurement will be performed in supine position. A facemask is placed over the nose and mouth of the child. SF₆, an inert gas, will be washed in until an equilibrium is established between in- and expiratory gas of a concentration of 4%. Then the washing out starts and will be finished if the concentration of SF₆ is 2.5% of the concentration after wash in. From this procedure LCI and FRC can be derived.

Chest CT scan

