In addition, if available as routine care in the local NICU/ high care centre, patients will be offered a free breathing volumetric chest CT scan without sedation at 6 months corrected age according to the local routine care protocol. (31). CT scans are scored by an experienced thoracic radiologist using the quantitative Perth-Rotterdam Annotated Grid Morphometric Analysis (PRAGMA)-BPD scoring method. (37) This scoring system identifies lung tissue with a normal appearance, hypoattenuation, hyperattenuation and bronchial wall thickening and expresses their volume in ml and as percentage of total lung volume. In addition, the severity of architectural distortion of the lung, meaning an abnormal displacement of bronchi, vessels, fissures and/or septa caused by diffuse or localized lung disease, will be scored.

Cardiac Ultrasound

If available as routine care, children will be screened for pulmonary hypertension by cardiac ultrasound at 6 months corrected age. For this echocardiogram, we will use an EPIC 7C (Philips Medical Systems, Best, the Netherlands) or Vivid E9 (GE Healthcare, Wauwatosa, WI, USA) ultrasound system. Apical 4-chamber, parasternal long-axis and short-axis views will be acquired and stored. M-mode, 2D, color Doppler and pulsed wave Doppler images will be acquired to collect data on tricuspid regurgitant jet, pulmonic valve insufficiency, pulmonary acceleration time, right and left ventricular (RV and LV) dimensions and mass, shortening fraction of the LV, and fractional area change (FAC) of the RV. All measurements will be performed off-line using Xcellera (version R4.1, Philips, Best, The Netherlands).

Costs

In between visits, a monthly electronic tailor-made diary will be provided to the parents to obtain data on hospital re-admissions, oxygen supplementation, unscheduled visits to health care providers, medication, absence from work and attendance of day care between the study visits. These data will be used for the cost-effectiveness analysis.

Informed consent for follow up studies

At the last clinic visit we will ask written informed consent for follow up studies.

Table

	Visit 0 months	Visit 6 months	Visit 12 months
Weight, height, head circumference	x	x	x
CarerQOL-7D*	x	x	x
IBQ-R	x	x	x
Multiple breath washout**		x	x
Chest CT scan**		x	
Cardiac ultrasound**		x	

*also measured monthly in an online diary, together with data on admissions and absence of work

** not mandatory, if available as routine care

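### Caregiver quality of life is analysed as a change score from an in-hospital baseline, which costs precision, and the monthly CarerQol scores have no stated role in comparing the arms

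*Protocol*

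**What the plan says.** Objective 2 (section 2) asks, among other things, whether the 95% limit gives caregivers a better quality of life. The relevant statements are:

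- **Analysis, section 10.2:** "Changes in the total score of the CarerQOL between baseline and 6 months and between baseline and 12 months will be assessed". Continuous secondary outcomes are to be analysed with linear mixed models. The only covariates named are BPD severity and weight at inclusion, and these are justified by their relevance to weight SDS.
- **Collection, section 8.3:** "This CarerQol will be assessed during all visits and online monthly". The footnote to the visit table repeats this: "also measured monthly in an online diary, together with data on admissions and absence of work".
- **Collection, Summary:** "The parents will be asked to fill in 2 questionnaires (CarerQOL and IBQ-R) at inclusion, 6 and 12 months", without mention of monthly scores. Of the diary it says: "Parents will have the possibility to record data on respiratory complaints, admissions, and absence from work in an online monthly diary".
- **Use of diary data, section 8.3 (Costs):** "These data will be used for the cost-effectiveness analysis". The items listed just before that sentence do not include the CarerQol.
- **Baseline setting, section 3:** infants are included at 36 to 38 weeks PMA, "when they are still admitted on the NICU or post-IC-high care units".
- **Possible arm difference, Summary:** "A disadvantage of the study may be that children in the high SpO₂ group will be longer on oxygen, whether in the hospital or at" (the sentence closes by naming the child's home).

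**The concern.** Section 8.3 describes the CarerQol as an instrument for the impact of giving informal care. At inclusion the infant is on a NICU or high-care unit, so the first score may predict later scores at home only weakly. The weaker that correlation, the more noise a subtraction adds.

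The two planned contrasts also look only at 6 and 12 months. According to section 9.2.2 the intervention ends two weeks after oxygen stops, so its most direct effect on carers falls while the child is on oxygen. If the arms differ in burden during those months and the difference has gone by 6 months, neither contrast can show it. The trial could then report no difference in caregiver quality of life although one existed for part of the first half-year, and although scores from that period had been collected.

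**Working it through.** The protocol gives no figure on this point to reproduce. The check has three parts.

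**1. Scores collected and scores used.** From inclusion at 36 to 38 weeks PMA to 6 months corrected age (40 + 26.09 weeks):

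- 66.09 − 36 = 30.09 weeks, about 6.9 months
- 66.09 − 38 = 28.09 weeks, about 6.5 months

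So about six monthly scores fall between baseline and the 6-month visit, and about five more before 12 months. The analysis in 10.2 names three time points: inclusion, 6 months and 12 months.

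**2. Subtracting or adjusting for baseline.** Let σ² be the variance of a CarerQol score, assumed equal at baseline and follow-up, and r the correlation between the two. The protocol does not give r, so a range is shown.

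- Change score: variance 2(1 − r)σ²
- Follow-up score adjusted for baseline: variance (1 − r²)σ²
- Ratio: 2(1 − r) / [(1 − r)(1 + r)] = 2 / (1 + r), which exceeds 1 for any r below 1

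| r (assumed) | Change score | Adjusted | Excess variance |
|---|---|---|---|
| 0.2 | 1.60 | 0.96 | 67% |
| 0.3 | 1.40 | 0.91 | 54% |
| 0.5 | 1.00 | 0.75 | 33% |
| 0.6 | 0.80 | 0.64 | 25% |

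The confidence interval is wider by the square root of the ratio: √1.67 = 1.29 at r = 0.2 and √1.25 = 1.12 at r = 0.6, so 29% to 12% wider.

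**3. A difference that fades before 6 months (illustration only).** Assumptions: a between-arm difference of 0.5 SD in the first k of six monthly scores and none afterwards; equal correlation ρ of 0.3 to 0.7 between all scores; complete diaries; no clustering; 90 per arm (half of the 180 in section 4.4); two-sided 0.05.

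- Change to 6 months: variance 2(1 − ρ). Its expected difference is 0 when k is below 6.
- Mean of six monthly scores, adjusted for baseline: variance (1 + 5ρ)/6 − ρ². Its expected difference is 0.5 × k/6.
- Example with ρ = 0.3 and k = 3: variance 2.5/6 − 0.09 = 0.327, standard error √(2 × 0.327/90) = 0.085, difference 0.25, ratio 2.93, power about 83%.

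| Months with a difference (k) | Power, change to 6 months | Power, six-month mean |
|---|---|---|
| 2 | 5% | 49–59% |
| 3 | 5% | 83–91% |
| 4 | 5% | 97–99% |
| 6 (still present at 6 months) | 81–99% | nearly 100% |

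The 5% is the significance level itself. Adjusting for baseline does not raise it, because the 6-month score then carries no difference to detect. Only scores from the earlier months can.

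**The case against.** The strongest reply is that nothing here is contradictory. Visits are at inclusion, 6 and 12 months, the Summary schedules the CarerQol at those times, and 10.2 analyses it there. Objective 2 asks about better quality of life, not about temporary burden during oxygen. Longer oxygen use would still be visible, since its duration and length of hospital stay are compared between arms as outcomes of their own. The diary is optional and burdened carers may skip entries, so relying on scheduled visits is defensible. All of this stands. It is why the 6- and 12-month contrasts should remain the planned ones, and why an average over diary scores, some recorded while infants are still admitted, should only support them.

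A second reply is that a linear mixed model need not mean plain subtraction. That is partly right. However, an arm-by-time contrast with baseline as a free response has, with complete data, the same variance as the change score. The gain comes only if baseline is a covariate or is constrained equal across arms, and 10.2 states neither. Because the arms are randomised, the in-hospital baseline affects precision and causes no bias.

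A reader might go further and infer that the arms are expected to differ during home oxygen and that the planned contrasts will therefore show nothing. The protocol does not support that. It says only that longer oxygen may be a disadvantage, adds that hospital stay did not differ in the earlier trial it cites, and gives no duration of home oxygen. If many infants are still on oxygen at 6 months, that visit captures the difference. Nor do the documents show that the monthly scores go unused altogether: they sit in the diary and may feed the cost-effectiveness analysis.

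**Conclusion.** The point holds as a weakness in how a secondary endpoint is fixed. It is not an error, and the primary result is untouched.

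The loss of precision from subtraction is present at any correlation below 1. Its size, 67% to 25% more variance, rests on assumed correlations of 0.2 to 0.6 and on equal variances at baseline and follow-up.

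The inability of the two planned contrasts to show a difference that ends before 6 months is a matter of logic. How likely such a difference is, and how large, cannot be derived from the protocol; the power figures only illustrate what the monthly scores could add. Because the protocol itself sets the contrast and the time points, this is more than a detail left to a statistical analysis plan.

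**What to change.** Change section 10.2 as follows.

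- Compare the CarerQol score between arms at 6 and at 12 months with the inclusion score as a covariate, in place of the change scores. Keep these as the planned contrasts.
- Estimate both from one repeated-measures mixed model that also includes the monthly scores.
- Pre-specify as a supporting contrast the average between-arm difference up to 6 months corrected age. Define the window by calendar time or corrected age, identically in both arms. It must not depend on how long each child receives oxygen, because the allocated arm affects that.
- Align the Summary with section 8.3 on whether the CarerQol is collected monthly.

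The cost is a few sentences and a slightly larger model; the scores are already being collected. The drawback is that monthly scores will be incomplete, so the supporting contrast relies on missing at random, which section 10 already assumes when more than 10% of data are missing. It will also mix scores from hospital and home. Diary completion should be reported by arm beside it.

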8.1.2 Secondary study parameters/endpoints (if applicable)

Secondary outcomes are rates of re-hospitalisations, quality of life of the caregivers (Dutch version of the CarerQOL questionnaire) (34) and infant stress (Infant Behaviour Questionnaire – Revised, IBQ-R) (35), length SDS and head circumference SDS at 6 months corrected age and weight SDS, length SDS, head circumference SDS at 12 months corrected age. Length of hospital stay and length of oxygen supplementation will be obtained from medical records. Also, respiratory symptoms and unscheduled health care visits to the emergency department, general practitioner or paediatrician will be secondary outcomes at all visits. Parents will also be asked to bring the growth chart ('groeiboekje') from the child consultation clinic to obtain basic growth data at earlier time points.

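### Infant stress is analysed as change in an undefined IBQ-R total that mixes distress with positive behaviour, and the baseline is subtracted rather than adjusted for

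*Protocol*

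**What the plan says.** Section 8.1.2 lists the secondary outcome as "infant stress (Infant Behaviour Questionnaire – Revised, IBQ-R"). Section 10.2 fixes how it is analysed: "changes in the total score of the IBQ-R between baseline and 6 months and between baseline and 12 months will be assessed". The model is stated generally: "All secondary parameters will be assessed by linear mixed effect models for continuous outcomes". The only covariates that section 10.2 names are BPD severity and weight at inclusion, and it justifies them by their relevance to weight SDS at 6 months. It does not mention a baseline questionnaire score.

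Section 8.3 says that the very short form is used and that it "is an instrument assessing 36 items on 3 broad scales of infant temperament". It continues: "The questionnaire assesses 6 domains: activity level, soothability, fear, distress to limitations, smiling and laughter and duration of orienting". Parents are asked to "rate the frequency of specific temperament-related behaviors observed over the past week". The questionnaire is given at all three visits. On the first of these, section 3 says that "patients will be included between 36 and 38 weeks PMA, when they are still admitted on the NICU or post-IC-high care units".

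Section 10.2 applies the same rule, change in total score from baseline to 6 and to 12 months, to the CarerQOL.

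**The concern.** There are two separate problems.

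The first is the score. An outcome called stress needs a number whose direction says more stress or less stress. The protocol describes three temperament scales and six domains, some about distress and some about positive or neutral behaviour. It then analyses one total without saying how that total is formed or which way it points. A reader of the final report could not tell whether a higher value is good or bad.

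The second is the contrast. The baseline rating covers a week in hospital before term age, and the follow-up ratings are made at 6 and 12 months corrected age. If the two are weakly correlated, subtracting the first from the second adds its variation to the outcome and removes little. The same loss applies to the CarerQOL whenever the baseline is subtracted without also being adjusted for.

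At stake are the interpretability of one secondary outcome and the precision of two.

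**Working it through.** The protocol gives no effect size, SD, correlation or power for the IBQ-R or the CarerQOL, so there is no stated figure to reproduce. The first step sets sections against each other. The others are algebra with assumed inputs.

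**Step 1. Sections side by side.**
- Sections 8.1.2 and 10.2: the construct is infant stress, and the score is a single total.
- Section 8.3: the construct is temperament, with three broad scales and six domains. Fear and distress to limitations are distress by name. Smiling and laughter, soothability, activity level and duration of orienting are not.
- No section defines a total, a direction, reverse scoring, or which scale stands for stress.

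**Step 2. What an unkeyed total can do.** Let three scales have unit SD, be uncorrelated and be added without reversal. The SD of the total is √3 = 1.73. Effects are in SD units (assumed).
- Distress falls by 0.4 and a positive scale rises by 0.4: the net effect is −0.4 + 0.4 = 0, and the total shows nothing.
- Only the distress scale moves, by 0.4: 0.4/√3 = 0.23.
- All three scales move by 0.4 in the same scored direction: 3 × 0.4/√3 = 0.69.

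The result therefore depends on keying and on which scales respond. The protocol settles neither.

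**Step 3. Change score against baseline adjustment.** Let baseline and follow-up have equal variance σ² and correlation r.
- Variance of the change score: 2σ²(1 − r).
- Residual variance after adjusting for baseline: σ²(1 − r²).
- Ratio: 2(1 − r)/(1 − r²) = 2/(1 + r).

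The inverse, (1 + r)/2, converts the 180 patients of section 4.4 into the number that would give the same precision under adjustment.

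| r (assumed) | Variance ratio 2/(1+r) | 180 × (1+r)/2 |
|---|---|---|
| 0 | 2.00 | 90 |
| 0.3 | 1.54 | 117 |
| 0.5 | 1.33 | 135 |

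Follow-up score alone has variance σ², so a change score is worse than ignoring the baseline when 2(1 − r) exceeds 1, that is, when r is below 0.5. Above 0.5 it is better than follow-up alone, but for any r below 1 it remains less precise than adjustment.

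**Step 4. The same in power, as an illustration only.** Assumptions: 90 per arm, two-sided 0.05, normal approximation, and a standardised effect borrowed from the primary endpoint in section 4.4, 0.5/1.18 = 0.42. Power = Φ(0.4237/(s√(2/90)) − 1.96), where s is √(2(1 − r)) for the change score, √(1 − r²) for adjustment and 1 for follow-up alone.

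| r (assumed) | Change score | Follow-up alone | Baseline-adjusted |
|---|---|---|---|
| 0 | 0.52 | 0.81 | 0.81 |
| 0.3 | 0.67 | 0.81 | 0.85 |
| 0.5 | 0.81 | 0.81 | 0.91 |

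**Step 5. Bias.** The baseline is taken at inclusion and the arms are randomised. A poor baseline therefore does not shift the expected difference between arms. It adds variance, and a missing baseline also leaves a child without a change score.

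**The case against.** The strongest reply is that the analysis plan, which is not shown, may supply the detail. Scoring direction and subscale rules are often left there, and having three scales does not rule out a summary score. Cancellation occurs only if items are summed without reversal. This stands in part: it shows that a meaningful total is possible. But section 10.2 does not leave the matter open. It fixes a total as the measure of stress, and even a fully keyed total would be a temperament summary in which distress is only part.

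A second reply is that assessing changes within a linear mixed model does not exclude adjusting for baseline, and that a change score with its baseline as covariate gives the same treatment estimate as the adjusted follow-up score. That is correct. The variance penalty applies only if the difference is analysed without the baseline score as a covariate, and section 10.2 names no such covariate. The reply also supports the fix.

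A third reply is that every IBQ-R number above is assumed. This stands too. Step 2 shows a total doing worse or better than a single scale depending on the inputs, so no particular loss of power from pooling can be attributed to this trial.

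A reader might infer that many items cannot apply to an admitted preterm infant, or that the instrument cannot measure stress. The protocol supports neither. It does not list the items, the validated age range or the handling of non-applicable items. Two domains are distress by name, and the ratings at 6 and 12 months are collected in any case. Nor does it show that a CarerQOL baseline taken in hospital reflects later home burden poorly. For the CarerQOL only the precision argument holds.

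**Conclusion.** The point holds as a fault in a stated rule. Section 10.2 commits infant stress to a total that the protocol does not define and that its own description of the instrument gives no clear stress direction. This part needs no assumption about effect sizes.

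The precision part holds for both questionnaires, conditional on the change being analysed without baseline adjustment. With equal variances at the two times and r assumed between 0 and 0.5, the change score carries 2.0 to 1.33 times the variance of the adjusted comparison. A low r for the IBQ-R is plausible from the infants' age and setting at inclusion but is not established by the document. The consequence is noise, not bias.

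This is a secondary outcome. It does not enter the sample size calculation, and the primary analysis of weight SDS is unaffected.

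**What to change.** In section 10.2:
- Replace the IBQ-R total with the instrument's own distress-related scale as the infant-stress outcome, and state its direction. The scale should come from the published scoring of the very short form and not be assembled ad hoc from domain names, because section 8.3 does not say which domains belong to which scale.
- Compare that scale between arms at 6 and at 12 months, with the inclusion score as covariate and not subtracted. If the instrument proves unusable at 36 to 38 weeks PMA, omit the inclusion score from the model.
- Report the other IBQ-R scales separately.
- Analyse CarerQOL as the follow-up score at 6 and at 12 months with its baseline as covariate.

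The cost is a change of wording, with no new data and no extra visits. The downside is that no single IBQ-R total is reported. The change should be made before outcome data are analysed, so that the choice of scale cannot be seen as driven by the results.
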